2.5 New Lesions

The appearance of new malignant lesions indicates disease progression; therefore, evaluation of new lesions is very important. Currently, there are no specific standards for imaging detection of lesions, yet the discovery of a new lesion should be clear. For instance, progression should not be attributed to differences in imaging technology, changes in imaging morphology, or other lesions outside of the tumor (e.g., some so-called new bone lesions are merely healing or recurrence of the original lesion).

This is particularly important when a patient's baseline lesions show partial or complete response. For example, necrosis of a liver lesion might be reported as a new cystic lesion on a CT scan, which it is not.

Lesions detected during follow-up that were not found during the baseline examination are considered new lesions and indicate disease progression. For example, a patient found to have visceral lesions at baseline, when undergoing a head CT or MRI examination, discovers metastatic foci; such intracranial metastatic lesions are considered evidence of disease progression, even if the patient did not have a head examination at baseline.

If a new lesion is ambiguous, such as due to its small size, further treatment

and follow-up evaluation are needed to confirm whether it is a new lesion. If repeated examinations confirm that it is a new lesion, then the time of disease progression should be counted from the time of its initial discovery.

Lesion assessment by FDG-PET generally requires additional testing for supplementary confirmation. It is reasonable to evaluate the progression in combination with FDG-PET and supplementary CT examination results (especially for new suspicious diseases). New lesions can be clearly identified by FDG-PET assessment, carried out according to the following procedure:

- If the baseline FDG-PET examination result is negative, and the subsequent follow-up FDG-PET examination is positive, it indicates disease progression.
- If no baseline FDG-PET examination was performed, and the subsequent FDG-PET examination result is positive:
- If the follow-up FDG-PET positive examination identifies new lesions that are consistent with the CT examination results, it proves disease progression.

If the positive findings from a follow-up FDG-PET scan cannot be confirmed by CT scan results, a further CT scan is required for confirmation (if confirmed, the progression date is counted from the abnormal findings of the previous FDG-PET scan).

If the positive findings from a follow-up FDG-PET scan correspond to lesions already identified by CT scan, and there is no progression of these lesions on imaging, then there is no disease progression.

2.6 Explanation of Assessment Missing and Non-evaluable

If imaging or measurement of a lesion cannot be performed at a specific time point, the patient is considered unevaluable at that time point. If only a portion of the lesions can be assessed during an evaluation, this situation is generally considered unevaluable at that time point, unless there is evidence to confirm that the missing lesions will not affect the efficacy response assessment at the designated time point.

2.7 Special Notes on Efficacy Assessment

When nodular lesions are included in the overall target lesion assessment and the size of these nodules decreases to a "normal" size (<10mm), they will still have a lesion size scan report. To avoid overestimating the situation reflected by the increase in nodule size, even if the nodule is normal, the measurement results will be recorded. As previously mentioned, this means that subjects with a complete response will not be recorded as 0 on the eCRF form.

If efficacy confirmation is required during the trial process, repeated "unevaluable" time points will complicate the best efficacy assessment. The trial's analysis plan must clarify how these missing data/assessments can be interpreted when determining efficacy. For example, in most trials, a subject's response of PR-NE-PR can be considered as having received efficacy confirmation.

When a subject experiences an overall deterioration in health that requires cessation of drug treatment, but without objective evidence, it should be reported as symptomatic progression. Even after treatment is discontinued, efforts should be made to assess the objective progression.

Symptomatic deterioration is not an assessment description of objective response; it is the reason for stopping treatment. The objective response of such subjects will be assessed through the target and non-target lesion conditions shown in Appendices 1 to 3.

Early progression, early death, and unevaluable situations are special cases of the study and should be clearly described in each protocol (depending on the treatment interval and treatment cycle).

In some cases, it is difficult to distinguish local lesions from normal tissue. When the assessment of complete response is based on such a definition, we recommend performing a biopsy before the efficacy assessment of complete response of local lesions. When some subjects' abnormal imaging results of local lesions are considered to represent lesion fibrosis or scar formation, FDG-PET is used as an assessment standard similar to biopsy for confirming complete response. In such cases, the application of FDG-PET should be

described prospectively in the protocol, and specifically for this situation.

The reporting of medical literature is used as support. However, it must be recognized that the limitations of FDG-PET and biopsy themselves (including the resolution and sensitivity of both) will lead to false-positive results in the assessment of complete response.

Appendix 1: Response at Time Point - Subjects with Target Lesions (Including or Excluding Non-target Lesions)

Target Lesions	Non-target	New Lesions	Overall
	Lesions		Response
CR	CR	None	CR
CR	Non-CR/Non-PD	None	PR
CR	Not evaluable	None	PR
PR	Non-progression or	None	PR
	not fully evaluable		
SD	Non-progression or	None	SD
	not fully evaluable		
Not evaluable	Non-progression	None	NE
PD	Any condition	Any condition	PD

Note: CR = Complete Response, PR = Partial Response, SD = Stable Disease, PD = Progressive Disease, NE = Not Evaluable.

Appendix 2: Response at Time Point - Subjects with Only Non-target Lesions

Non-target Lesions	New Lesions	Overall Response
CR	None	CR
Non-CR or Non-PD	None	Non-CR or Non-PD
Not evaluable	None	Not evaluable
Indeterminate PD	Yes or No	PD

Note: For non-target lesions, "Non-CR/Non-PD" refers to an effect better than SD. Since SD is increasingly used as an endpoint for evaluating efficacy, the efficacy of Non-CR/Non-PD is established to target cases where no lesions are measurable.

For unclear findings of progression (such as very small uncertain new lesions;

cystic changes or necrotic changes in existing lesions), treatment can continue until the next assessment. If progression is confirmed at the next assessment, the progression date should be the date when suspected progression first appeared.

Appendix 3: Best Overall Response Requiring Confirmation for CR and PR Efficacy

First Time Point	Subsequent Time Point	Best Overall
Overall Response	Overall Response	Response
CR	CR	CR
CR	PR or SD or PD	SD if SD lasts long
		enough, otherwise PD
CR	PD	If SD lasts for a sufficient duration, then SD; otherwise, PD
CR	NE	If SD lasts for a sufficient duration, then SD; otherwise, NE
PR	CR	PR
PR	PR	PR
PR	SD	SD
PR	PD	If SD lasts for a sufficient duration, then SD; otherwise, PD
PR	NE	If SD lasts for a sufficient duration, then SD; otherwise, NE
NE	NE	NE

Note: CR stands for Complete Response, PR for Partial Response, SD for Stable Disease, PD for Progressive Disease, and NE for Not Evaluable. Superscript "a": If a true CR occurs at the first time point, and any disease progression occurs at subsequent time points, then even if the subject's response meets the PR criteria relative to baseline, the response evaluation at later time points is still PD (because the disease will reappear after CR). The best response depends on whether SD occurs within the shortest treatment

interval. However, sometimes the first evaluation is CR, but subsequent scans suggest that small lesions still appear, thus the subject's response at the first time point should actually be PR rather than CR. In this case, the initial CR judgment should be changed to PR, and the best response is PR.

2.8 Efficacy Assessment/Confirmation of Response Duration

2.8.1 Efficacy Confirmation

For non-randomized clinical studies with tumor response as the primary endpoint, it is necessary to confirm the efficacy of PR and CR to ensure that the efficacy is not the result of an evaluation error. In studies with stable disease or disease progression as the primary endpoints, efficacy confirmation is no longer required, as it does not have value for the interpretation of the trial results. In the case of SD, at least one measurement that meets the SD criteria specified in the protocol should be made within the shortest time interval after the start of the trial (generally not less than 6 to 8 weeks).

2.8.2 Overall Response Duration

The overall response duration is the time from the first measurement that meets the CR or PR criteria (whichever is measured first) to the first true record of disease recurrence or progression (using the smallest measurement value recorded in the trial as the reference for disease progression). The overall complete response duration is the time from the first measurement that meets the CR criteria to the first true record of disease recurrence or progression.

2.8.3 Stable Disease Duration

The duration from the start of treatment to disease progression, using the smallest sum in the trial as the reference (if the baseline sum is the smallest, it serves as the reference for calculating PD). The clinical relevance of the stable disease duration varies depending on different studies and different diseases. If the study endpoint is to maintain the proportion of patients with the shortest duration of stable disease, the protocol should specify the minimum time interval between the two measurements defined for SD (Stable Disease).

Note: The duration of response, stable period, and PFS (Progression-Free

Survival) are influenced by the frequency of follow-up after baseline evaluation. The definition of standard follow-up frequency is not within the scope of this guideline. The frequency of follow-up should take into account many factors, such as the type and stage of the disease, the treatment cycle, and standard protocols. However, if comparisons between trials are to be made, the limitations of the accuracy of these measurement endpoints should be considered.

Appendix 4: Quality of Life Scoring

EORTC QLQ-C30 (Version 3.0 Chinese)

We are very interested in learning about you and your physical condition. Please answer the following questions personally and circle the answer that best suits you. There are no "right" or "wrong" answers; simply circle the one that applies to you.

The information you provide will be kept strictly confidential.

Patient's Signature:

Date of Birth: /

Date of Completion: /

1: *Not at all* 2: *A little* 3: *Quite a bit* 4: *Very much*

- 1. Do you have difficulty doing some strenuous activities, such as lifting heavy shopping bags or suitcases? 1 2 3 4
- 2. Do you have difficulty walking long distances? 1 2 3 4
- 3. Do you have difficulty walking short distances outside? 1 2 3 4
- 4. Do you need to lie in bed or stay in a wheelchair during the day? 1 2 3 4
- 5. Do you need help with eating, dressing, washing, or using the toilet?

In the past week

6. Have you been limited in doing your work or other daily activities? 1 2 3 4

7. Have you been limited in pursuing your hobbies or other leisure activities? 1 2 3 4

78

- 8. Do you experience shortness of breath? 1 2 3 4
- 9. Have you had pain? 1 2 3 4
- 10. Do you need to rest? 1 2 3 4
- 11. Do you have trouble sleeping? 1 2 3 4
- 12. Do you feel weak? 1 2 3 4
- 13. Do you lack appetite? 1 2 3 4
- 14. Do you feel nauseated? 1 2 3 4
- 15. Have you vomited? 1 2 3 4
- 16. Have you had constipation? 1 2 3 4
- 17. Have you had diarrhea? 1 2 3 4
- 18. Do you feel fatigued? 1 2 3 4
- 19. Does pain interfere with your daily activities? 1 2 3 4
- 20. Do you have difficulty concentrating on things, such as reading newspapers or watching TV? 1 2 3 4
- 21. Do you feel nervous? 1 2 3 4
- 22. Do you feel anxious? 1 2 3 4
- 23. Do you get irritable easily? 1 2 3 4
- 24. Do you feel depressed? 1 2 3 4
- 25. Have you had any memory difficulties? 1 2 3 4
- 26. Has your physical condition or medical treatment interfered with your family life? 1 2 3 4
- 27. Has your physical condition or medical treatment interfered with your social life? 1 2 3 4
- 28. Has your physical condition or medical treatment caused you financial difficulties? 1 2 3 4

For the following questions, circle the number from 1 to 7 that best matches your answer.

29. How would you rate your overall health status last week?

1234567

Very poor - Very good

30. How would you rate your overall quality of life last week?

1234567

1. Quality of Life Scoring Instructions:

The EORTC's QLQ-C30 (Version 3.0) is a core questionnaire for all cancer patients, with a total of 30 items. Items 29 and 30 are divided into seven levels, which are scored from 1 to 7 based on the response options; the other items are divided into 4 levels: Not at all, A little, Quite a bit, and Very much, and are directly scored from 1 to 4 points.

2. Calculation of EORTC QLQ-C30 Domain (Dimension) Scores (Raw Score): For the convenience of statistical analysis and application, the questionnaire is often divided into certain domains. A domain is an aspect of the quality of life constitution, also known as a dimension, and is treated as an independent variable during analysis.

The 30 items of the EORTC QLQ-C30 (Version 3.0) can be divided into 15 domains, including 5 functional domains (physical, role, cognitive, emotional, and social functioning), 3 symptom domains (fatigue, pain, and nausea/vomiting), 1 overall health status/quality of life domain, and 6 single items (each as a domain). The classification is shown in the table below.

To obtain the score (raw score RS) for a domain, add up the scores of the items included in the domain and divide by the number of items included, i.e., RS = (Q1 + Q2 + ... + Qn) / n.

EORTC QLQ-C30 Domain Classification

Physical Functioning	5	1-5
Role Functioning	2	6-7
Emotional Functioning	4	21 - 24
Cognitive Functioning	2	20 - 25
Social Functioning	2	26 - 27
Global Health Status	2	29 - 30
Fatigue	3	10, 12, 18
Nausea and Vomiting	2	14 - 15
Pain	2	9, 19
Dyspnea	1	8
Insomnia	1	11

Appetite Loss	1	13
Constipation	1	16
Diarrhea	1	17
Financial Difficulties	1	28

3. Calculation of EORTC QLQ-C30 Standardized Scores

To enable comparison of scores across domains, a linear transformation using the range method is further applied to convert raw scores into standardized scores ranging from 0 to 100. Additionally, the transformation serves another purpose, which is to change the direction of the scores. Since the QLQ-C30 scale, except for items 29 and 30, consists of reverse items (the higher the score, the worse the quality of life), the scoring rules explicitly state: for functional domains and the global health status domain, a higher score indicates better functioning and quality of life, while for symptom domains, a higher score indicates more symptoms or problems (worse quality of life). Therefore, when calculating the standardized scores for functional domains, the direction must also be changed. Specifically, the calculations are as follows (where R represents the score range for each domain or item):

Functional Domains: $SS=[1-(RS-1)/R]\times 100SS=[1-(RS-1)/R]\times 100$

Symptom Domains and Global Health Status Domain:

 $SS=[(RS-1)/R]\times 100SS=[(RS-1)/R]\times 100$

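### Appendix 4 lists Cognitive Functioning as two items but writes them as the range 20 to 25, which overlaps Emotional Functioning; the entry should read 20, 25

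*Protocol*

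**What the plan says.** Protocol Appendix 4 prints the questionnaire and then its scoring instructions. It states that "The 30 items of the EORTC QLQ-C30 (Version 3.0) can be divided into 15 domains" and gives a table with one row per domain: name, number of items, item numbers. The row at issue is "Cognitive Functioning 2 20 - 25". The row just above it is "Emotional Functioning 4 21 - 24".

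For the raw score, the instruction is to "add up the scores of the items included in the domain and divide by the number of items included". Items other than 29 and 30 "are directly scored from 1 to 4 points". A linear transformation is then meant to "convert raw scores into standardized scores ranging from 0 to 100", with the direction reversed for functional domains.

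Section 9.2 makes QLQ-C30 quality of life a secondary endpoint and compares scores with baseline by paired t-tests or Wilcoxon signed-rank tests. Appendix 4 says each domain is analysed as a variable in its own right.

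**The concern.** The row disagrees with itself and with the rest of the table. Elsewhere a hyphen marks a run of consecutive items, as in "Physical Functioning 5 1-5", and non-adjacent items are separated by commas, as in "Fatigue 3 10, 12, 18" and in the Pain row (9, 19). On that convention the cognitive row names six items while counting two, and four of the six belong to another domain.

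This appendix is the protocol's operative scoring rule for a named endpoint. If the item column is programmed literally, the cognitive score is mostly a mood score, and a change in mood from baseline would appear as a change in cognition. The values would look plausible, so a range check would not catch them.

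**Working it through.** **Step 1. Count the items in each row**, taking a hyphen as an inclusive range and a comma as a list.

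- Hyphenated rows: 1-5 (5 stated, 5 listed), 6-7 (2, 2), 21-24 (4, 4), 26-27 (2, 2), 29-30 (2, 2), 14-15 (2, 2), and 20-25 (2 stated, 6 listed).
- Comma rows: Fatigue (3, 3) and Pain (2, 2).
- Six single-item rows: all match.

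Fourteen of 15 rows agree with their count; only Cognitive Functioning does not.

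**Step 2. Compare the totals** (physical, role, emotional, cognitive, social, global, fatigue, nausea/vomiting, pain, single items).

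- Stated counts: 5 + 2 + 4 + 2 + 2 + 2 + 3 + 2 + 2 + 6 = 30, which reproduces the protocol's figure.
- Listed items: 5 + 2 + 4 + 6 + 2 + 2 + 3 + 2 + 2 + 6 = 34. The surplus of four is items 21 to 24, used twice.
- With the cognitive row read as items 20 and 25, the total is 30 and each of items 1 to 30 is used exactly once.

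**Step 3. Check the item content.** In the printed questionnaire, item 20 asks about concentration and item 25 about memory. Items 21 to 24 ask about feeling nervous, anxious, irritable and depressed.

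**Step 4. Score both readings with the protocol's formulas.** RS = sum of items / number of items. For functional domains SS = [1 − (RS − 1)/R] × 100, with R = 4 − 1 = 3.

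| Items 20 and 25 | Items 21-24 | Two-item SS | Six-item RS | Six-item SS | Difference |
|---|---|---|---|---|---|
| 1 | 1 | 100 | 6/6 = 1 | 100 | 0 |
| 1 | 3 | 100 | 14/6 = 2.33 | 55.6 | −44.4 |
| 3 | 1 | 33.3 | 10/6 = 1.67 | 77.8 | +44.4 |
| 1 | 4 | 100 | 18/6 = 3 | 33.3 | −66.7 |
| 4 | 1 | 0 | 12/6 = 2 | 66.7 | +66.7 |

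**Step 5. Find the general size.** The six-item mean weights the pair by 2/6 and the emotional items by 4/6. So six-item SS = (1/3) × cognitive SS + (2/3) × emotional SS, and its departure from the two-item score is (2/3) × (emotional SS − cognitive SS). Both scores lie in 0 to 100, so the largest departure is (2/3) × 100 = 66.7. Enumerating all 4^6 = 4096 answer patterns gives the same maximum.

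The same identity applies to change from baseline. If items 20 and 25 stay at 1 while items 21 to 24 move from 1 to 2, the two-item score stays at 100 but the six-item score falls from 100 to 77.8.

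**The case against.** The strongest reply is that the appendix corrects itself. The count of two, the 30-item total, the adjacent row claiming 21 to 24 and the wording of items 20 and 25 all point to the same pair. Four other hyphenated rows (6-7, 14-15, 26-27, 29-30) have two items and read equally well as a pair or as a range; only 1-5 and 21-24 force the range reading. The cognitive entry may simply be that pair style carried over by mistake. This stands as far as weight goes: a careful programmer would score the domain correctly. It does not make the entry right, because the Pain row shows that the table writes a non-adjacent pair with a comma.

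A reader might go further and infer that the table produces impossible scores. Summing six items and dividing by the listed 2 gives RS from 3 to 12 and SS from 33.3 down to −266.7, with 4068 of the 4096 patterns negative. The document does not support that as its own result. Its rule divides by the number of items included, so six summed items require a divisor of 6. The out-of-range values come from taking the items from one column and the divisor from another. That misapplies the rule and would show up at once against the stated 0 to 100 scale.

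It is also fair that the 44- and 67-point differences come from constructed answer patterns. Where emotional and cognitive scores agree, the six-item mean equals the intended score. Nothing in the protocol says how far they will differ in these patients.

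**Conclusion.** The entry is wrong as written and needs a minor correction. Read literally and scored by the protocol's own rule, it turns the cognitive score into one-third cognition and two-thirds emotional functioning, with an error of up to 66.7 points for an individual patient and no out-of-range value to reveal it.

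The effect is conditional on someone programming the item column literally, and it is confined to one of 15 domains of a secondary endpoint. The primary endpoint and the sample size are not affected. The protocol does not show that the domain has been or will be mis-scored.

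The conclusion assumes that the hyphen is in the source document and was not introduced when the text was extracted. That cannot be fully excluded, but hyphens and commas are kept distinct in the neighbouring rows.

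**What to change.** In the Appendix 4 domain table, change the Cognitive Functioning items to 20, 25 and keep the count of 2. Optionally, have the scoring program confirm that the 15 domains use each of the 30 items exactly once. That check would detect this overlap; a check for scores outside 0 to 100 would not.

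The cost is one table entry and, if wanted, one line of checking. Data collection, visits and patients are not affected.
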